#### **12.3.2 Subjects Exiting the Study Due to IUD Expulsion:**

In addition to Sections 12.3 and 12.3.1, when a subject is exiting the study due to an IUD expulsion, the following will be performed:

- A urine pregnancy test will be done approximately 6-8 weeks after the exit visit by the subject at home, with a follow up call by the study coordinator or PI required to document results.

#### **12.3.3 Monthly Contact (Up to 52 Weeks $\pm$ 1 w)**

Subjects will be contacted each month from the time of IUD insertion, to confirm completion of the monthly e-diary for:

- The need for additional contraception (If a subject believes the study device may have been expelled or is no longer in place, the subject should call for an urgent study visit and refrain from having sex or use appropriate non-hormonal contraception until further evaluation is completed. (See Section 4.7 for details);
- Use of emergency contraception;
- Documentation of menstrual and intermenstrual bleeding;
- Documentation of menstrual pain or cramping

Additionally, the following will occur during the monthly contacts:

- Assess if there have been any adverse events since the last contact;
- Use of concomitant medications;
- Collection of any missing diary information (frequency of intercourse, pain with intercourse and use of concomitant or emergency contraception); and
- Resolution of any prior serious adverse events or adverse events.

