#### **6.4 Safety Review**

The Medical Monitor will evaluate safety and pregnancies on an ongoing basis and significant findings will be addressed immediately. A monthly safety and pregnancy review will occur with the Study Principal Investigator to review safety trends, including pregnancies. The medical monitor, the responsible project team and Sponsor personnel will review study drug-related findings periodically and at least bi-monthly. Additional details are located in the Medical Monitoring Plan. If the Medical Monitor identifies any safety issues that may alter the risk benefit ratio of the study product, the Medical Monitor will immediately inform the project team and the Sponsor.

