### **12.3 Visits 3-6 Follow-up (Week 6±1w, 13±2w, 26±2w and 52±2w/)**

The subject will return for follow up visits at preplanned intervals following placement of the LevoCept. At these follow up visits, the following will be performed:

- Vital signs and weight
- Pelvic exam (string check)
- Pregnancy test, urine
- Transvaginal ultrasound (if indicated)
- Concomitant contraception
- Need for contraception (If a subject believes the study device may have been expelled or is no longer in place, the subject should call for an urgent study visit and refrain from having sex or use appropriate non-hormonal contraception until further evaluation is completed. (See Section 4.7 for details)
- Interval and concurrent medications
- Adverse events
- E-diary review with subject
- Verify sexual activity and any back-up method is documented
- Instruct the subject to contact the site immediately if she thinks she has become pregnant.

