## **13. Diaries**

Subjects will be instructed to complete diaries daily. Diaries are designed to collect the following information for each day of the 28-day cycle:

- Day of cycle
- Absence or presence of menstrual or other bleeding (none, spotting, normal or heavy)
- LevoCept expulsion (yes, no, suspected)
- Usage of additional birth control methods and type of birth control used
- Presence of menstrual pain or cramping
- Frequency of intercourse
- Pain with intercourse

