### 15.2 Definition of An Adverse Event

An **adverse event** is any untoward medical occurrence in a clinical investigation subject administered an investigational product and which does not necessarily have to have a causal relationship with this treatment. An AE can, therefore, be any unfavorable and unintended sign (that could include a clinically significant abnormal laboratory finding), symptom, or disease temporally associated with the use of a medicinal product, whether or not considered related to the medicinal product.

- Any medical condition or clinically significant laboratory abnormality with an onset date before the first date of attempted study device placement is usually considered to be pre-existing, and should not be documented in the eCRF as an AE, unless there is an increase in frequency or intensity of that AE, but should be recorded as medical history.
- Any AE (i.e., a new event or an exacerbation of a pre-existing condition) with an onset from the first attempt of study device placement through Study Exit should be recorded as an AE on the eCRF. All AEs must be recorded on the AE eCRF regardless of the severity or relationship to study device. It is important that Investigators also report all AEs that result in expulsion or removal of the investigational product being studied, whether serious or non-serious.

Pregnancy is an outcome, and not an adverse event in this study.

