	YYYY-MM-DD	xx	xx	xx	Heavy Bleeding	Yes	No	Not Applicable	Yes	Yes	Male condom with Spermicide		Yes	Yes
	YYYY-MM-DD	xx	xx	xx	None		Yes	No Pain	Yes	Yes	Withdrawal			
	YYYY-MM-DD	xx	xx	xx	None		Yes	Moderately Painful	No	No	Other, specify			
	YYYY-MM-DD	xx	xx	xx	None			Very Painful	No	No				
xxx-xxx					None						Hormonal contraception/			
	YYYY-MM-DD	xx	xx	xx			Yes	No Pain	Yes	Yes	Other, specify	None	No	No
					Spotting						Female barrier/			
	YYYY-MM-DD	xx	xx	xx			Yes	No Pain	Yes	Yes	Male condom with Spermicide	Mild	No	No
Program Location: \\xx\xxx\xxx\xxx\xxxxxx\xxxxxxxxxxxxxxxxxxx\xxxx\xxxxx.sas							date	time						

CONFIDENTIAL

Sebela Pharmaceuticals Development LLC
CMDOC-0022

Page x of y

Listing 16.2.8.2
Subject Missed Diary Review (All Enrolled Subjects)

Subject ID	At least one Diary Missed	Date of Missed	Sequence #	CRF Cycle #	Cycle #	Day #	Vaginal intercourse	Additional Birth Control [1]	Pain[2]	Pain Worse[3]
xxx-xxx	Yes	YYYY-MM-DD	xx	xx	xx	xx	Yes	Yes	No Pain	Yes
	Yes	YYYY-MM-DD	xx	xx	xx	xx	Yes	No	Some Pain	No
	Yes	YYYY-MM-DD	xx	xx	xx	xx	Yes	Yes	Painful	Yes
xxx-xxx	Yes	YYYY-MM-DD	xx	xx	xx	xx	Yes	Yes	Moderately Painful	Yes
	Yes	YYYY-MM-DD	xx	xx	xx	xx	No		Not Applicable	No
	Yes	YYYY-MM-DD	xx	xx	xx	xx	Yes	Yes	Very Painful	Yes
xxx-xxx	No									

[1] If yes, did the subject use any additional birth control methods?

[2] Did the subject experience pain during intercourse?

[3] If the subject experienced pain during intercourse, was the pain worse than before IUD insertion

Program Location: \\xx\xxx\xxx\xxx\xxxxxx\xxxxxxxxxxxxxxxx\xxxx\xxxxx.sas date time

CONFIDENTIAL

Sebelo Pharmaceuticals Development LLC
CMDOC-0022

Page x of y

Listing 16.2.8.3
Monthly Phone Contact (All Enrolled Subjects)

Subject ID	Contact Conducted	Date of Contact	Cycle #	Intercourse[1]	Additional Birth Control [2]	Medications[3]	Adverse Events[4]	Resolve or Change[5]
xxx-xxx	Yes	YYYY-MM-DD	xx	Yes	Yes	Yes	Yes	Yes
		YYYY-MM-DD	xx	No	No	No	No	No
		YYYY-MM-DD	xx	Yes	Yes	Yes	Yes	Yes
xxx-xxx	No							
xxx-xxx	Yes	YYYY-MM-DD	xx	Yes	Yes	Yes	Yes	Yes
		YYYY-MM-DD	xx	No	No	No	No	No
		YYYY-MM-DD	xx	Yes	Yes	Yes	Yes	Yes

[1] Did subject have intercourse at least one time during the previous Cycle?

[2] Did the subject use any additional forms of birth control or emergency contraception during the previous Cycle?

[3] Has subject taken any medications since the last contact?

[4] Did subject experience any Adverse Events since the last contact?

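### Pregnancy is the primary outcome, but no Year-1 monthly contact or diary item asks about it directly, so a non-ectopic pregnancy that begins and ends between urine tests is captured only by self-report or indirectly.

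*Protocol*

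**What the plan says.** **Monthly contact.** Protocol 12.3.3 uses the contact to confirm that the diary is complete on contraception, emergency contraception, bleeding and cramping. Staff then "Assess if there have been any adverse events since the last contact", ask about medications, follow up earlier events, and fill diary gaps: "Collection of any missing diary information (frequency of intercourse, pain with intercourse and use of concomitant or emergency contraception); and". Pregnancy is not on the list. SAP Listing 16.2.8.3 shows five questions for this contact: intercourse ("Did subject have intercourse at least one time during the previous Cycle"), additional or emergency contraception, medications, adverse events ("Did subject experience any Adverse Events since the last contact") and change in earlier events.

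**Diary.** Protocol section 13 states: "Diaries are designed to collect the following information for each day of the 28-day cycle". Its seven items, and QS1–QS10 in SAP Listing 16.2.8.1, cover bleeding, pain, intercourse, contraception and expulsion, but not pregnancy.

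**Adverse-event definition.** Protocol 15.2: "Pregnancy is an outcome, and not an adverse event in this study". Two other places qualify this. Section 15.1 makes ectopic pregnancy a serious adverse event, and section 20.7 includes intrauterine pregnancy among the adverse events to receive special attention.

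**Testing.** Table 1 schedules urine tests on Day 1 and at weeks 6, 13, 26 and 52, and leaves the monthly-contact cell blank. A home test follows 17 days after removal or exit, and another 6–8 weeks after an exit for expulsion.

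**Self-report.** At placement (12.2) and at Visits 3–6 (12.3) the site is told: "Instruct the subject to contact the site immediately if she thinks she has become pregnant".

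**The concern.** The Pearl Index numerator in SAP 4.1 is a count of pregnancies, and the planning case expects one. For that count to be complete, each pregnancy must meet a test, a question or a report. A pregnancy that ends early, by loss or termination, may leave a negative urine test at the next visit. If nobody asks about it in the meantime, the woman remains in the evaluable population, which requires only one report of pregnancy status, and her cycles stay in the denominator as pregnancy-free.

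The error runs in one direction. A missed pregnancy can only lower the Pearl Index and the life-table rate, which flatters the device. The study has a single arm, so no comparator shares the bias.

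**Working it through.** **1. The plan's own figure.** Inputs: 1 pregnancy and 2,015 evaluable cycles (protocol Sample Size; SAP 3.2). Formula (SAP 4.1): pregnancies × 1300 / cycles.

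1 × 1300 / 2,015 = 0.645, which rounds to the stated 0.6.

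The stated interval is (0.1, 3.3). No method is named, and an exact Poisson interval on 2,015 cycles gives 0.02–3.59. That mismatch is a separate matter and does not bear on this point. The exact interval is used below.

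**2. Effect of missing the one pregnancy**, with 2,015 cycles held fixed:

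| Pregnancies counted | Pearl Index | Exact 95% CI |
|---|---|---|
| 1 | 0.65 | 0.02–3.59 |
| 0 | 0 | 0–2.38 |

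Each uncounted pregnancy lowers the index by 0.65, which here is the whole planned estimate.

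**3. Gaps between scheduled tests.** Counting from Day 1, the gaps are 6, 13 − 6 = 7, 26 − 13 = 13 and 52 − 26 = 26 weeks. At the extremes of the visit windows the last gap is (52 + 2) − (26 − 2) = 30 weeks.

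**4. Share of conceptions that overlap no scheduled test.** Assumptions, none of them from the documents:
- conception time t is uniform over weeks 0–52;
- a pregnancy that ends early is urine-positive from t + 2 to t + D weeks, with D = 8 or 12;
- the woman is followed to Week 52.

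A test at week w then catches conceptions with t between w − D and w − 2.

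*D = 8, device continued:* caught intervals are 0–4, 5–11, 18–24 and 44–50, so 4 + 6 + 6 + 6 = 22 weeks. Missed: (52 − 22)/52 = 57.7%.

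*D = 12, device continued:* caught intervals are 0–11 (the first two tests merge), 14–24 and 40–50, so 11 + 10 + 10 = 31 weeks. Missed: (52 − 31)/52 = 40.4%.

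*Exit at Week 52:* the home test at 52 weeks plus 17 days also catches t from 50 to 52, adding 2 weeks. Missed: 28/52 = 53.8% (D = 8) or 19/52 = 36.5% (D = 12).

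The range is therefore about 37–58%. It applies only to pregnancies that end early. It becomes undercounting only for those that also go unreported and do not surface indirectly, and the documents give neither share.

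**The case against.** The case against has several sound parts, and they limit what can be claimed.

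- **A reader might infer that such a pregnancy is counted only if the woman volunteers it.** The documents do not support that. She is told repeatedly to call, and the monthly contact asks about adverse events and medications, which could bring out the symptoms, complications or treatment of a loss. Bleeding and cramping are recorded daily, and visits include a string check. These routes are indirect: protocol 6.2 lists amenorrhea and irregular bleeding as anticipated events, so symptoms may be put down to the device, and the instruction to call is not worded for a pregnancy that has already ended.
- **A reader might infer that the adverse-event question excludes all pregnancy by definition.** It does not. Ectopic pregnancy is a serious adverse event (15.1), and 20.7 lists intrauterine pregnancy, in tension with 15.2. That tension is itself a reason not to rely on the adverse-event question.
- **A reader might infer that the safety reviews have no pregnancy data.** Section 6.4 says "A monthly safety and pregnancy review will occur with the Study Principal Investigator to review safety trends, including pregnancies". That review can use visit tests and reported pregnancies, and the committee trigger in 20.8 responds to reports. What they lack is a routine monthly query.
- **A reader might infer that one missed event decides the trial.** The plan states no formal sample size calculation, hypothesis or success threshold for the Pearl Index, so a miss changes an estimate and its interval, not a pass or fail.
- **The illustrated share is not an estimate of bias.** Women who leave before Week 52 have an exit urine test and a later home test, which the calculation omits, so the share is too high for them.
- **The contact form itself is not available.** The five questions come from a listing layout. The text of 12.3.3 is the firmer evidence, and it too contains no pregnancy item.

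**Conclusion.** The gap is real but modest: in Year 1 nothing between visits asks directly about pregnancy. A non-ectopic pregnancy that begins and ends between scheduled tests depends on instructed self-report or on indirect information. The direction of any bias is certain (downward), while its size cannot be estimated from the documents. The 37–58% rests on the assumed detection window, evenly spread conceptions and follow-up to Week 52. The move from 0.65 to 0 shows how sensitive a count of about one is to a single miss. This is a cheap improvement to how the primary endpoint is ascertained, not a flaw that invalidates the analysis.

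**What to change.** Add one yes/no item to the monthly contact in protocol 12.3.3 and its form: *Since the last contact, have you had a positive pregnancy test, suspected a pregnancy, or had a pregnancy end?* Add the same item to the end-of-cycle contact in 12.4.1, which lists only sexual activity and back-up contraception while office tests are six months apart.

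A yes goes to the existing confirmation steps in section 18 and the Pregnancy Notification form. A confirmed pregnancy enters the SAP 4.1 numerator under the existing conception-date rule, so the endpoint definition does not change.

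The cost is a minor wording and form change on contacts already made, with no new visit or scheduled test, plus a few false suspicions to check. The Pearl Index might come out slightly higher. Pregnancies that the woman never recognised would still be missed.

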#### **12.4 Long-term Follow-up, post 52-weeks visit (Every 6 Months: Months 18-30 ( $\pm 4$ wks) and 3 yrs ( $-3$ wks/ $+4$ wks))**

At 52 weeks, subjects will be allowed to continue with the study device with a follow-up office visit every 6 months for a maximum of three years post study device placement. During these visits, the following will be performed:

- Vital signs and weight
- Pelvic exam (string check)
- Transvaginal ultrasound If unable to confirm IUD placement by string check or if indicated
- Pregnancy test, urine
- Interval and concurrent medications
- Adverse events
- Concomitant contraception
- Need for contraception (If a subject believes the study device may have been expelled or is no longer in place, the subject should call for an urgent study visit and refrain from having sex or use appropriate non-hormonal contraception until further evaluation is completed. (See Section 4.7 for details)
- Verify sexual activity and any back-up method is documented
- Instruct the subject to contact the site immediately if she thinks she has become pregnant.

##### **12.4.1 End of Each 28-day Cycle Contact (Post 52 Weeks + 1 w)**

Subjects will be contacted (e.g. phone calls, e-mail or text message) at the end of each 28-day cycle, beginning after the 52-week visit. Cycles are determined from the day of LevoCept insertion:

- Verify sexual activity
- Document any back-up contraception methods

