#### **4.7 LevoCept Retention Compliance**

Subjects will be instructed on how to check for study device presence by feeling for the strings in the vagina. Subjects will not be required to routinely check for study device presence, but if a subject believes the study device may have been expelled or is no longer in place, the subject can check for the study device string if desired. If the subject does not feel the strings, feels more than the strings, or has expelled the study device, the subject should be instructed to call for an urgent study visit and refrain from having sex or use appropriate non-hormonal contraception until further evaluation is completed. For detailed instructions regarding management of missing strings, refer to the Study Reference Manual.

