**Table 1. Study Schedule of Assessments**

	Visit 1 - Screening	Visit 2 - (LevoCept Placement) Day 1	Visit 3 - Follow up Week 6 ± 1w	Visit 4 - Follow up Week 13 ± 2w	Visit 5 - Follow up Week 26 ± 2w	Visit 6 - Follow up Week 52 ± 2w/	Monthly Contact up to 52 Weeks ± 1 w	Exit Visit (Visit 2 – Visit 6/Week 52)	Long Term Follow up Every 6 Months - post 52 Weeks (max 3 yrs. post Insertion) ± 2 w	End of each 28-day Cycle Contact (Post 52 Wks ± 1w)	Exit Visit (Post Visit 6/Week 52 – Year 3)
CONTRAMED											
Initiation/Subject Characteristics											
Assessment of Eligibility	X	X									
Distribution of information	X										
Informed consent, PHI and Bill of Rights forms	X										
Demographics and baseline characteristics	X										
Medical/surgical, gynecologic and menstrual history	X										
Safety and Effectiveness											
Vital signs and weight	X	X	X	X	X	X		X	X		X
Height	X										
General physical exam	X					X		X			X
Pelvic exam	X	X	X 	X 	X 	X 		X 	X 		X 
Cervical cytology	X 										
Cervical infection test (gonorrhea and chlamydia)	X 										
Transvaginal ultrasound (for verifying study device position)		X	X 	X 	X 	X		X	X 		X
Pregnancy test-urine	X	X	X	X	X	X		X 	X		X 
Prior and interval concurrent medication	X	X	X	X	X	X	X	X	X		X
Adverse events		X	X	X	X	X	X	X	X		X
Other											
IUD placement		X									
IUD placement ease		X									
IUD placement pain		X									
IUD removal ease								X			X
IUD removal pain								X			X
Concomitant contraception		X	X	X	X	X	X	X	X	X	X
Need for contraception	X	X 	X 	X 	X 	X 	X	X 	X 	X 	X 
Patient trained on E-diary	X 	X	X	X	X						
E-diary reviewed with subject		X 	X	X	X	X	X				
End of study medication								X			X

**Note:** Screening and enrollment visit *may be combined* if the patient requests and all labs and screening exams are documented as normal.

1. Pelvic exam for LevoCept string check
2. Transvaginal Ultrasound performed at Visit 6 or Exit visit or if indicated

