6.2.9.7 Device Expulsion and Removal

Device expulsion will be recorded daily by the subject in e-diary. Device removal procedure will be recorded in the CRF. Cumulative study device removal rates and expulsion rates will be summarized at 1-year (study day 1 - 364), 2-year (study day 365 - 728), and 3-year (study day 729 +).

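### After Week 52 the 28-day contact has no adverse event or medication item, so scheduled AE questioning drops from about every 4 weeks to about every 26 weeks at the 12-month line the AE onset tables use

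*Protocol*

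**What the plan says.** **Year 1.** Protocol 12.3.3 requires a contact each month. Among its tasks is: "Assess if there have been any adverse events since the last contact". It also covers concomitant medications and the resolution of earlier events. Protocol Table 1 and SAP Table 3 mark the adverse event and medication rows in the monthly-contact column.

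**Years 2-3.** Protocol 12.4 provides a "follow-up office visit every 6 months for a maximum of three years post study device placement", and AEs and medications are reviewed at those visits. Between visits, Protocol 12.4.1 states: "Subjects will be contacted (e.g. phone calls, e-mail or text message) at the end of each 28-day cycle, beginning after the 52-week visit". The items listed are "Verify sexual activity" and "Document any back-up contraception methods". In the 28-day column of Protocol Table 1 and SAP Table 3 the adverse event and medication rows are empty. The rows for concomitant contraception and need for contraception are marked, the latter with footnote 8 on suspected expulsion. Section 12.4.1 does not list need for contraception.

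**Analysis.** SAP 6.2.9.1 summarises AEs by onset at 0-3, >3-6, >6-12 and >12 months, and Table 14.3.1.13 has those columns. Table 14.3.1.1.1 also breaks between Day 364 and Day 365. For expulsion, SAP 6.2.9.7 states: "Device expulsion will be recorded daily by the subject in e-diary". It reports cumulative rates for each of the three years.

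**The concern.** The method of collecting AEs changes at Week 52, and the AE onset tables split at the same point. In year 1 a woman is asked about events every month. Afterwards she is contacted just as often, but the schedule asks about events only at the 6-monthly visits. Mild events that start and resolve between visits are the ones most likely to be forgotten or misdated over half a year.

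A lower count after 12 months could then mean that the device is better tolerated with time, that fewer women remain, or that the question was asked less often. The tables cannot separate the last explanation from the first. What is at stake is the reading of longer-term tolerability, in a study meant to support a longer Phase III trial.

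**Working it through.** The plan states no figure for this point, so there is none to reproduce. The check compares the schedules and works out the intervals.

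**1. Is the omission consistent?**

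| Place | Year-1 monthly contact | 28-day contact after Week 52 |
|---|---|---|
| Protocol text | AEs, medications, resolution of earlier events (12.3.3) | sexual activity, back-up contraception (12.4.1) |
| Protocol Table 1, AE row | marked | blank |
| Protocol Table 1, medication row | marked | blank |
| SAP Table 3, AE and medication rows | marked | blank |

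Text and both tables agree, so this is not a slip in one place.

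**2. Contacts without an AE item.** SAP Table 2 assigns cycles 14 to 39 to years 2-3 (days 365-1092).
- Number of contacts = 39 - 13 = 26; equivalently (1092 - 364)/28 = 26.
- Two of these, at days 728 and 1092, fall one day before a target visit. The other 24 do not.

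**3. Scheduled visits with an AE item.** SAP Table 1 target days are 365 (Visit 6), then 547, 729, 912 and 1093.
- Gaps: 547 - 365 = 182; 729 - 547 = 182; 912 - 729 = 183; 1093 - 912 = 181 days.
- Visits after Week 52: 4.

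**4. Change in the scheduled look-back.**
- Against a 28-day interval: 182/28 = 6.5 times.
- Against a calendar month: 182/(365/12) = 6.0 times.

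**5. Longest gap between consecutive long-term visits, with windows.**
- ±2 weeks (Table 1): 26 + 2 + 2 = 30 weeks, or 210 days.
- ±4 weeks (heading of 12.4): 26 + 4 + 4 = 34 weeks, or 238 days.

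The two places give different windows for the same visits, which must be reconciled.

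**6. After the fix.** With the AE item on the existing 28-day contact, the scheduled look-back in years 2-3 returns to 28 days with no added contact.

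**7. What cannot be computed.** The documents give no rate at which AEs are missed at 6-month recall, so the number of unrecorded events is unknown.

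**The case against.** **Lighter follow-up may be deliberate.** Subjects are followed for 12 months for the protocol endpoints, and continuation is optional. The two items in 12.4.1 are what is needed to decide whether a cycle counts in the Pearl Index. AEs must still be recorded through study exit, are asked about at every long-term and exit visit, and can surface at unscheduled visits. This stands as an explanation, but it does not make collection alike on the two sides of month 12.

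**The question may already be asked.** Listing 16.2.8.3 (Monthly Phone Contact) covers all enrolled subjects with no year-1 limit. Its intercourse and birth-control questions match 12.4.1, and it also asks about medications, new AEs and changes in earlier AEs. The listing index has no separate entry for the 28-day contact. This stands: the documents do not say whether the form is used after Week 52. If it is, the schedules are wrong and data collection is sound.

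**The tables are not formal comparisons.** SAP 6.2.9 plans no inferential safety analysis. The onset columns span 3, 3, 6 and up to 24 months over one fixed denominator, so they are not like-for-like rates anyway. This stands, and limits the consequence to interpretation.

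**A stronger reading about expulsion is tempting.** A reader might infer that expulsion in years 2-3 also rests on 6-month recall, since "Subjects will not be required to routinely check for study device presence", and that up to 26/4 = 6.5 cycles per silent expulsion would be miscounted because of the thinner contact. The documents do not support this:
- Each long-term visit has a string check, with ultrasound if placement is not confirmed. That is examination, not recall.
- Protocol 4.7 and 12.7 tell a woman who suspects expulsion to contact the site at once.
- Table 1 marks need for contraception, with the suspected-expulsion footnote, at the 28-day contact. The year-1 contact handles expulsion through the same item.
- Protocol 13 sets a daily diary with an expulsion item and no Week 52 stop, and SAP 4.1 runs the diary to study exit.
- In year 1 the Week 26 and Week 52 string checks are also 26 weeks apart. The 6.5-cycle exposure is therefore not created at Week 52, and asking about suspected expulsion would not find one that is unsuspected.

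What remains on expulsion is disagreement between passages. Section 12.4.1 omits an item that Table 1 marks. Table 1 schedules no diary review after Visit 6 and the year-1 contacts, and 12.4 and 12.4.1 never mention the diary, yet SAP 6.2.9.7 relies on it for the 2- and 3-year rates.

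**Conclusion.** The point holds for scheduled AE and medication questioning. As written, the interval rises from about 4 weeks to about 26 weeks after Week 52 (6 to 6.5 times), with 26 contacts lacking an AE item and 4 visits that have one, for a woman who stays to the end of year 3. A fall in AEs with onset after 12 months would partly reflect less frequent asking. How large that part is cannot be derived from the documents.

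This assumes that the schedules describe what is done, so that the Listing 16.2.8.3 form is not in use after Week 52. The safety tables are descriptive, and the 12-month Pearl Index is not touched. It is a change worth making because it is cheap, not a flaw in the main result. On expulsion, the conclusion goes no further than the need to reconcile the passages.

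**What to change.** 1. Add to Protocol 12.4.1, and to the 28-day column of Protocol Table 1 and SAP Table 3, the items already in 12.3.3 and on the Listing 16.2.8.3 form: any AE since the last contact, change or resolution of earlier AEs, and new medication. If that form is already used after Week 52, correct the text and both schedules to say so.
2. Reconcile 12.4.1 with the need-for-contraception mark in Table 1.
3. State whether the daily e-diary continues after Week 52, reconciling Protocol Table 1, 12.4 and 12.4.1 with Protocol 13 and SAP 4.1 and 6.2.9.7. Then name the expulsion data source after Week 52 in SAP 6.2.9.7. Listing 16.2.5.2 already carries expulsion before the visit and its date.
4. Reconcile the long-term visit window between Table 1 and 12.4.

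**Cost.** Short amendment wording and a few more questions at a contact already planned, on an existing form, with no new visit or procedure. More minor AEs will be recorded in years 2-3. If the items start partway through the extension, the report should give the date, because collection would then differ within years 2-3.
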